Study Protocol

Effect of Locally-Applied Simvastatin on Clinical Attachment Level and Alveolar Bone in Periodontal Maintenance Patients

[figure not shown]
NCT: 03452891

March 3, 2022

Patient Population

This one year, randomized, and double-masked clinical trial was conducted from March 2019-December 2020. Fifty patients, who were receiving periodontal maintenance therapy at the University of Nebraska Medical Center (UNMC) College of Dentistry were screened and identified by faculty and investigators involved in this study (RR, AK, MC and HR). Assessment included a review of medical and dental histories and previous oral hygiene and periodontal charting. Inclusion criteria for the study included subjects between the ages of 40-85 years, a periodontal diagnosis of advanced chronic periodontitis (stage III-IV, Grade B (Tonetti et al. 2018)), one quadrant with at least three posterior teeth and one 6-9 mm periodontal pocket with a history of BOP and no radiographic vertical bony defect ≥ 1.5 mm, overall good systemic health, and a history of regular PMT. Exclusion criteria consisted of subjects with systemic diseases that significantly affect periodontal inflammation and bone turnover (e.g., chronic use of steroids or non-steroidal anti-inflammatory drugs, estrogens, bisphosphonates, calcitonin, methotrexate, antibiotics, >325 mg aspirin/day), surgical periodontal therapy within the past year, and pregnant or breast-feeding females. Patients who met the inclusion criteria had the protocol explained and had all questions answered prior to obtaining consent.

Figure 1: Study Design Flowchart

Data Collection

Clinical measures and gingival crevicular fluid (GCF) collection were collected by one of three calibrated dentists (RR, AK, and RH). During GCF collection, experimental site (6-9 mm interproximal pocket with no vertical bony \geq 1.5 mm, and history of bleeding on probing) was isolated with cotton rolls and gently dried with gauze. Supragingival plaque was removed from the test with a dental explorer. For GCF collection, an absorbent paper strip (PerioPaper Strips, Oraflow, Hewlett, NY) was inserted into the facial and lingual/palatal sulcus of the experimental site (Figure 2). After 30 seconds, the paper strips were immediately placed into a sterile vial and frozen at -80°C until further analysis. Strips contaminated by blood were discarded and were retaken after two minutes. Next, supragingival plaque, recession, probing depths, and bleeding on probing (BOP) within 30 seconds were recorded on 6 sites (MF, F, DF, ML, L, DL) on the experimental tooth and adjacent tooth.

Treatment Protocol

After the clinical data and GCF collection was completed, the investigator involved with data collection left, and the surgical / drug application phase of treatment was completed by a single clinician (LK, MB) and assistants (MC, LA) not involved with clinical measurements as described previously (Jasa et al. 2020). Following administration of local anesthesia to the experimental site, a #12B blade was used to reflect both the facial and lingual/palatal papilla including in the experimental 6-9 mm interproximal pocket. Interproximal soft tissue was removed to allow access to the root. To measure activation of gene markers of inflammation and bone turnover, an approximately 2x2x2 mm piece of the interproximal tissue was placed in a sterile vial of 1.5 mL RNA*later* solution (ThermoFisher Scientific, Waltham, MA) (Figure 3) and frozen at -20°C until further analysis. Scaling and root planning was performed interproximally on the test site and on the adjacent interproximal tooth surface. Verification

of a clean and smooth root surface was done using an 11/12 explorer and the Perioscope (Perioscopy Unit, Zest Dental Solutions, Carlsbad, CA) by the clinician (Figure 4).

After mechanical therapy was completed, the unmasked clinician (LK or MB) randomly assigned patients to test simvastatin in methylcellulose (SIM/MCL) or control (MCL) groups. The root surface was etched for 2 minutes with ethylenediaminetetraacetic acid (EDTA, Pref-Gel, Straumann, Andover, MA) followed by irrigation with sterile saline. SIM and MCL were prepared by local compounding pharmacy (Pharmacy Solutions Lincoln, NE) and mixed immediately prior placement to achieve 2.2 mg simvastatin (SIM) suspended in 0.15 ml methylcellulose gel (MCL) (test group) or 0.15 ml of methylcellulose gel alone (control group)(Figure 5).

Gels were placed at the base of the pocket and deposited up the interproximal root surface of the experimental tooth (Figure 6). The papilla were re-approximated under pressure and sealed using cyanacrylate (PeriAcryl, Glustitch, Delta, BC, Canada). Routine periodontal maintenance therapy (PMT) then was completed by MC or LA, including full mouth periodontal charting, debridement, and root planing of inflamed pockets avoiding the experimental area. Patients were instructed to avoid brushing and flossing of the experimental site for 6 weeks. They were dispensed Listerine (Johnson & Johnson Consumer, Inc., New Brunswick, New Jersey) and instructed to be used twice a day for 30 seconds for 6 weeks. Patients were asked to return for postoperative visits after 2 and 6 weeks along with PMT recalls at 3, 6, 9, and 12 months. GCF collection was repeated at 2- weeks and 12-month PMT visits and clinical measurements were repeated at 12 months (Figure 7) by one of the three calibrated examiners (AK, RR, and HR). Collection of approximately 2x2x2 mm interproximal tissue was repeated at 2 weeks by either LK or MB. During the 6-week follow up, patients were given Gel-Kam® preventative treatment gel (Colgate Oral Pharmaceuticals, NY, NY) and a GUM® Proxabrush® (Sunstar Americas, Inc., Schaumburg, IL) and patients were instructed to brush the experimental site twice a day using the provided

interproximal brush. Participants were questioned about adverse events at 2-weeks and 6-months, and 12-months PMT visits.

Figure 2: Baseline GCF Sample

Perioscope use

Figure 3: Baseline Interproximal tissue

Figure 4:

Figure 5: Mixing SIM & MCL

Figure 6: Placement of SIM

Figure 7: 12-months post-therapy

Analysis of GCF samples

Each GCF sample containing two paper strips was eluted using 85 μ l of 1 \times PBS by gently agitating the samples on a rocker plate for 1 h at 4°C. Analyte concentrations were measured using magnetic bead panels (Millipore, Billerica, MA) and read on a MAGPIX with Luminex xPONENT software (Luminex Corporation, Austin, TX) per the manufacturers' recommendations.

Nine analytes were measured: Fibroblast growth factor (FGF-2), interleukin (IL)-1 β , IL-6, IL-10, IL-17A, insulin-like growth factor 1 (IGF-1), tumor necrosis factor (TNF)- α , receptor activator of nuclear factor kappa-B ligand (RANKL), and vascular endothelial growth factor A (VEGF-A). The amounts of cytokines are reported in picograms per ml, then mathematically adjusted by multiplying 0.085 to achieve pg per sample.

Analysis of interproximal tissue samples

Interproximal tissue samples were collected between the interproximal sulcus of the experimental site and adjacent tooth and were stored in 1.5 mL RNA/*later* solution (ThermoFisher Scientific, Waltham, MA). RNA extraction was conducted using the NucleoSpin RNA XS—complete kit for isolation and purification of total RNA from extremely small samples (Marcherey – Nagel, [Düren, Germany](#)). DNA digestion and cDNA synthesis were done using the QuantiTect Reverse Transcription Kit from QIAGEN© (Germantown, MD) per the manufacturers' recommendations.

Samples were diluted with water and placed in 96-well custom array plates in technical triplicate; qPCR was executed with SsoAdvanced Universal SYBR Green Supermix from Bio-Rad (Hercules, CA) reagents. PCR conditions were 39 cycles at 95°C for 3 minutes (1 cycle) 95°C for 15 seconds, and at 58°C for 30 seconds (39 cycles). At the end point of rt-PCR analysis, the threshold cycle

or $\Delta\Delta Ct$ values were recorded. To analyze the relative changes in gene expression, the $2^{\Delta\Delta Ct}$ method was done, as described by Livak et al (2001).

Statistical analyses

A sample size of 22 per group was needed to achieve at least 80% power to detect a difference of 1.0 mm in clinical attachment level between groups with a common estimated group standard deviation of 1.1 mm with a significance level of 0.05 using a two-sided two-sample t-test. This is based on mean data from most relevant previous studies (Killeen et al., 2012 and Jasa et al., 2019).

For the experimental interproximal treatment sulcus, BOP was considered present at baseline if at least one buccal or lingual interproximal site had the condition present. The follow-up variables for BOP were determined as follows: if the patient started without BOP and ended without BOP or showed a reduction (i.e. presence of BOP at baseline to absence of BOP at 12 months), that patient was considered to have a good outcome. If the patient began with BOP and showed no improvement or they developed BOP, that patient was considered to have a poor outcome. Associations between categorical variables were assessed using Chi-Square tests, or Fisher's exact tests when expected cell counts were low. Medians and inter-quartile ranges (IQRs; the range of the middle 50% of the data (25th percentile, 75th percentile)) were calculated for each treatment condition, and Wilcoxon Rank Sum tests were used to examine differences in distributions of BOP between the two treatment conditions (i.e. SIM/MCL or MCL) for baseline BOP values. For the change in BOP outcome, logistic regression models were used, which included group and adjusted for worst side. Adjusted odds ratios are presented with 95% confidence intervals.

Descriptive statistics for raw GCF and RT-PCR continuous data are given as medians and interquartile ranges (IQRs, representing the range of the middle 50% of the data). For analysis, data was log transformed due to skew.

General estimating equations were run with each measure of interest as the outcome, and each model included the variables (analyte) group and time, as well as the interaction between group and time to assess if change over time differed by group. If the interaction was not significant, main effects models were run. P-values for post hoc comparisons were adjusted using simulation methods. Pearson correlations were also run to assess for association between GCF and interproximal tissue samples at a given time point. Clinical attachment level (CAL) change between baseline and 12-months was the primary clinical outcome measure for this clinical trial. For change in CAL baseline CAL values were subtracted from 12 months CAL value, and difference scores were plotted against GCF and rt-PCR measures at two weeks (i.e. > negative values indicate reduction in clinical attachment loss). Associations between change in CAL and measures at 2-weeks were assessed using Pearson correlations. All analyses were performed using SAS software version 9.4 (SAS Institute Inc., Cary, NC).

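### The 2-week tissue may be cut by a clinician who knows the patient's arm, and the arm is disclosed a step earlier than the procedure needs

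*Combined protocol and SAP*

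**What the plan says.** The Patient Population section describes the design: "This one year, randomized, and double-masked clinical trial was conducted". It does not say which parties are masked.

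The Treatment Protocol section gives the assignment rule: "After mechanical therapy was completed, the unmasked clinician" (one of two named clinicians) "randomly assigned patients to test simvastatin in methylcellulose (SIM/MCL) or control (MCL) groups". The next sentence begins "The root surface was etched for 2 minutes" and goes on to saline irrigation. Gel mixing, placement and closure of the papilla follow. The gel is described as mixed just before it is placed.

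The same section says of the follow-up sample: "Collection of approximately 2x2x2 mm interproximal tissue was repeated at 2 weeks by either" of those same two clinicians.

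Three safeguards are also stated. The examiner who takes the baseline measurements leaves before the surgical phase. The treating clinician and assistants take no part in clinical measurement. One of three calibrated examiners makes the 12-month measurements.

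**The concern.** The trial keeps treatment and clinical measurement apart, but the 2-week tissue falls on the treatment side of that line. It is an outcome sample collected by one of two people described as unmasked. qPCR is objective once the sample exists, but the assay cannot correct for where or how deep the cut was made. If knowledge of the arm influences the cut, the expression results shift in one direction by arm. A larger sample would not reduce that shift, and the planned models have no term that could remove it.

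The second, smaller matter is timing. As written, the arm is known during etching and irrigation, although neither step depends on it.

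**Working it through.** No figure in the plan bears on this point, so the check is a reading of the stated steps, followed by a look at where an arm-dependent cut would enter the analysis.

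**Steps in the order described (Data Collection and Treatment Protocol sections)**

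| Step | Done by | Could the arm be known? |
|---|---|---|
| Baseline GCF and clinical measures | Calibrated examiner, who then leaves | No, precedes assignment |
| Baseline tissue, scaling and root planing, check of the root surface | Treating clinician | No, precedes assignment |
| Assignment | Treating clinician, unmasked | Disclosed here |
| Etching for 2 minutes, irrigation | Treating clinician | Yes as written, but not needed |
| Mixing and placing gel, closure | Treating clinician | Yes, unavoidable with chairside mixing |
| 2-week GCF | Calibrated examiner | Not by role |
| 2-week tissue | Either of the two treating clinicians | Possibly |
| 12-month CAL | Calibrated examiner | Not by role |

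Two rows show exposure that the procedure does not require: etching with irrigation, and the 2-week tissue.

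**Where the 2-week tissue is used (Statistical analyses section).** Expression data are log transformed and modelled on group, time and their interaction. In symbols,

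E[log Y] = β0 + β1·group + β2·time + β3·(group × time).

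Baseline tissue is cut before assignment, so knowledge of the arm cannot affect it. Suppose knowledge of the arm shifts the 2-week log expression in the simvastatin arm, relative to control, by b. The interaction then estimates β3 + b. The shift falls wholly on the term that tests whether change over time differs by group.

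**Correlation with CAL change.** The plan does not say whether the Pearson correlations are run within arm or pooled. If they are pooled over two equal arms, the covariance is the within-arm covariance plus ½ × ½ × (arm difference in expression) × (arm difference in CAL change). A sampling shift b therefore adds ¼ × b × (arm difference in CAL change). This is zero if the arms do not differ in CAL change, or if the correlations are run within arm. The pooled correlations between GCF and tissue at 2 weeks are open to the same effect.

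**Size.** The documents give nothing from which b could be estimated: no between-sampler variability, no record of who sampled whom, and no expression SD.

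**The case against.** The strongest reply is that the main safeguards are already in place. Assignment comes late, after debridement and verification. Treatment and measurement teams are separate, and other people measure the primary outcome. All of this stands, and it confines the point to secondary data.

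The reply continues that the cut is not free: the section on analysis of interproximal tissue samples fixes the site between the experimental site and the adjacent tooth. This narrows the sampler's choice. It does not remove it, since the size is approximate and no depth or orientation is given. It is also fair that the sampler need not be the person who treated that patient. The text permits either clinician, so the exposure is possible rather than certain.

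On etching, the duration is fixed and its place after assignment is inferred from the order of sentences in a narrative. Any gain from changing it is small.

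Four stronger readings are tempting, and the documents do not support them.

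- *The double-masked label is contradicted.* It can mean patient and examiner, and an unmasked operator is compatible with that.
- *Recruiters knew past assignments.* One person is listed both as a screener and as an assistant in the treatment phase, but only the clinician is called unmasked. Nothing says that assistants learn the arm.
- *Allocation was unconcealed or predictable.* The text does not describe how the sequence was generated or held, the design flowchart is not shown, and the treatment procedure refers to an earlier publication. Who makes the assignment does not show who held the list. Any proportion of predictable assignments would rest on an assumed blocking scheme that the plan never mentions.
- *The false-positive rate for CAL is inflated by a known amount.* With 22 per arm and a two-sided 5% t-test, assumed shifts of 0.1, 0.2 and 0.3 SD would raise the rate to 6.2%, 9.9% and 16.3%. Those shifts are invented inputs that would give the same result for any alleged bias in any trial of this size. They do not measure an effect of tissue sampling, and separate examiners measure CAL.

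**Conclusion.** The point holds in a limited form. The 2-week tissue is an outcome sample that may be taken by someone who knows the arm. It supports the group-by-time gene-expression comparison and the correlations with CAL change, so those results carry an avoidable risk of bias. Etching and irrigation with the arm known is a minor, easily removed exposure. The primary CAL comparison is largely protected from assessment bias and is not called into question here.

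The size of the bias cannot be estimated from the documents and may be nil. The conclusion assumes that the order of sentences reflects the order of steps, and that nothing in the figure not shown or the cited earlier report keeps the 2-week sampler unaware of the arm. The first assumption affects only the etching point.

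**What to change.** For a trial run to this plan:

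1. Disclose the assignment only when etching and irrigation are complete, immediately before the gel is mixed. The treatment steps stay as they are and only the moment of disclosure moves. There is no cost, and the gain is small. If this was already the practice, correct the text.
2. Have the 2-week tissue taken by whichever of the two existing clinicians did not treat that patient, without access to that patient's allocation. No staff or procedures are added. The downside is some scheduling effort, because the other clinician must be available at the 2-week visit.

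The Patient Population section dates the trial March 2019 to December 2020, so for this trial the remedy lies in reporting:

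1. Record for each 2-week sample whether the sampler was the treating clinician and, if not, whether the sampler had access to the allocation.
2. Run the gene-expression comparison with all samples, and again without those taken by the treating clinician. The second run has fewer samples and wider intervals. It should be read as a check on direction and size, not as a second test. If the treating clinician took every sample, the check is not possible and only the limitation can be stated.
3. State the limitation beside the gene-expression results and the correlations with CAL change, and say which parties were masked.

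The cost is a search of treatment records and one extra model run per gene.

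### No adverse-event question is stated at week 6, the first visit after the repeat tissue sample; the next stated question is at month 6, about 24 weeks after the sample

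*Combined protocol and SAP*

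**What the plan says.** All the relevant text is in the Treatment Protocol section of the combined protocol and SAP, apart from the trial dates and the flowchart caption.

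- Visits: "Patients were asked to return for postoperative visits after 2 and 6 weeks along with PMT recalls at 3, 6, 9, and 12 months".
- Repeat sampling: "Collection of approximately 2x2x2 mm interproximal tissue was repeated at 2 weeks".
- Home care up to week 6: "Patients were instructed to avoid brushing and flossing of the experimental site for 6 weeks".
- Week 6: the section records that supplies were handed out ("During the 6-week follow up, patients were given" a gel and an interproximal brush) and that "patients were instructed to brush the experimental site twice a day using the provided" brush. It mentions no adverse-event question.
- Adverse events: "Participants were questioned about adverse events at 2-weeks and 6-months, and 12-months PMT visits".

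No other part of the available text describes how adverse events were collected, and the Statistical analyses section describes no analysis of them. The Patient Population section carries the caption "Figure 1: Study Design Flowchart", but the figure itself is not shown. The same section describes the trial as finished: "This one year, randomized, and double-masked clinical trial was conducted from March 2019-December 2020".

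**The concern.** The repeat tissue sample is an invasive study procedure at a site treated two weeks earlier. The week-2 adverse-event question falls at the same visit as the sample. Whether it was asked before or after the sampling, it cannot pick up what the sample leads to later. The natural place to ask is the next visit, week 6. The patient is then in the clinic and is being given new instructions for that same site, so a question would need no extra attendance.

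Under the stated list, a patient who had a brief problem between weeks 2 and 6 is next asked at month 6. Recording it then depends on recall over several months or on the patient having raised it unprompted, and the available text states no procedure for unprompted reports. At stake is how complete the safety record is, and so what a later statement of few or no adverse events would rest on.

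**Working it through.** **Inputs** (all from the Treatment Protocol section): visits at weeks 2 and 6 and months 3, 6, 9 and 12; repeat tissue sample at week 2; stated questions at week 2, month 6 and month 12. The plan gives no interval length of its own to reproduce, so this is date arithmetic on its schedule, with visits assumed to fall exactly on time.

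**Conversion.** 1 month = 365.25 / 12 / 7 = 4.348 weeks. Month 3 = 13.04, month 6 = 26.09, month 9 = 39.13 and month 12 = 52.18 weeks.

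**Visits against questions**

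| Visit | Week | Question stated? |
|---|---|---|
| Week 2 (repeat sample) | 2 | Yes |
| Week 6 | 6 | No |
| Month 3 | 13.04 | No |
| Month 6 | 26.09 | Yes |
| Month 9 | 39.13 | No |
| Month 12 | 52.18 | Yes |

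**Intervals between stated questions**

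- Treatment to week 2: 2.0 weeks
- Week 2 to month 6: 26.09 − 2 = 24.1 weeks
- Month 6 to month 12: 52.18 − 26.09 = 26.1 weeks

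**Age of an event in weeks 2 to 6 at the next stated question**

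- Event at week 2: 26.09 − 2 = 24.1 weeks
- Event at week 6: 26.09 − 6 = 20.1 weeks

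**With a question added at week 6**

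- Event at week 2: 6 − 2 = 4.0 weeks
- Event at week 6: 6 − 6 = 0 weeks
- In each case the question comes 26.09 − 6 = 20.1 weeks sooner

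**With a question at all six visits**, the intervals are 2.0, 4.0, 13.04 − 6 = 7.0, and then 13.0, 13.0 and 13.0 weeks. The longest falls from 26.1 to 13.0 weeks.

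**Sensitivity to the month convention.** If six months is 26 weeks, the gap from sample to next stated question is 26 − 2 = 24 weeks. With four-week months it is 24 − 2 = 22 weeks. The conclusion does not depend on the choice, and the decimals carry no weight.

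The documents give no event rate and no measure of recall loss, so a number of missed events cannot be derived.

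**The case against.** The strongest reply is that this is a preference, not a fault. Week 2, month 6 and month 12 is a stated schedule, the documents set no standard that it fails, and the month-6 question may cover everything since week 2. That stands. There is no uncovered time as such, only a long recall period, and the lag figures measure delay, not harm.

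A second reply is that the point argues from silence in an incomplete text. Figure 1 could list further questioning, and pages not available here could tell patients how to report problems. That stands as a limit on certainty. However, the section gives an explicit list of three time points, and any fuller schedule elsewhere would have to be reconciled with it.

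Third, the questioning sentence is loosely written. It groups week 2 with the maintenance visits, although the visit list calls it postoperative, and it may be a slip for weeks 2 and 6 and month 12. This cannot be ruled out, but it is speculation against the literal reading. Asking the sponsor to confirm the schedule settles it.

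Fourth, a week-6 question could not capture events caused by the gel and brush that start at that visit. That is correct: month 3 would be the first opportunity for those, which is a reason to ask there too. The case for week 6 rests on the week-2 sample.

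Finally, the trial is over, so missed events cannot be recovered. That is also correct, and it limits the remedy to confirmation and reporting.

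**Conclusion.** The point holds as a minor, inexpensive improvement. As written, the plan states no adverse-event question at the first visit after the repeat tissue sample, and the next stated question follows the sample by about 24 weeks (22 to 24.1 by month convention). A brief event in weeks 2 to 6 would first meet a stated question 20.1 weeks later than it would with a question at week 6.

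The consequence is a risk of under-ascertainment in both groups. No difference between groups is shown, and nothing here affects the analysis of clinical attachment level or the sample size. The conclusion assumes that the sentence on questioning means what it says, that Figure 1 adds no further time points, and that visits fell close to schedule.

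**What to change.** In a plan of this kind: put the same adverse-event question at all six scheduled visits. Week 6 is the most useful addition, and months 3 and 9 complete the set. The cost is three short questions per patient with their data entry, and no extra visit.

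For this completed trial: the sponsor should check Figure 1 and the visit forms, confirm at which visits patients were asked, and state that schedule in the report. If the three stated time points are confirmed, any safety statement should say that the period after the week-2 sample was first asked about at month 6. This costs a short check and a sentence or two. It does not recover events that were never asked about.

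### Does the missing minus sign in the gene-expression formula reverse the tissue results?

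*Combined protocol and SAP*

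**What the plan says.** In *Analysis of interproximal tissue samples*, the qPCR output is described as the threshold cycle "or $\Delta\Delta Ct$ values were recorded". The next sentence gives the calculation: "To analyze the relative changes in gene expression, the $2^{\Delta\Delta Ct}$ method was done". It adds that the "method was done, as described by" a published methods paper. No equation is written out. ΔCt, ΔΔCt, the order of subtraction, the reference gene or genes and the calibrator are not defined.

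In *Statistical analyses*, RT-PCR values are summarised on the raw scale ("Descriptive statistics for raw GCF and RT-PCR continuous data are given as medians and interquartile ranges") and then analysed on another: "For analysis, data was log transformed due to skew". Each measure enters a GEE model with group and time, "as well as the interaction between group and time to assess if change over time differed by group". Tissue values are used in two further places. One is the correlation with crevicular fluid: "Pearson correlations were also run to assess for association between GCF and interproximal tissue samples at a given time point". The other is the comparison with attachment-level change, where "difference scores were plotted against GCF and rt-PCR measures at two weeks" and Pearson correlations are computed. The primary outcome is the 12-month change in clinical attachment level, which does not involve the formula.

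**The concern.** A threshold cycle counts the doublings needed to reach a fixed signal, so more starting template gives a smaller number. Relative expression must therefore fall as the cycle count rises. Under the common convention of sample minus calibrator, this puts a minus sign in the exponent, and the text shows none.

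If an analyst followed the printed symbol with that convention, genes switched on by simvastatin would be reported as switched off, and the reverse. The log transform would carry the wrong sign into the GEE coefficients and into every correlation that involves tissue. Because p-values would not move, nothing in the test output would give the error away. Direction is what the tissue samples were taken to show, so this would matter for the mechanistic part of the trial.

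The undefined calibrator adds a second worry. If each patient's own baseline were the calibrator, every baseline value would equal 1, and the baseline visit would have no variance in the group-by-time model.

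**Working it through.** The plan gives no fold-change figure to reproduce, so the check is algebra plus one illustrative simulation.

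**1. Order of subtraction.** With perfect doubling, starting quantity is proportional to 2^(−Ct). Take ΔCt = Ct(target) − Ct(reference).

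- Sample minus calibrator: D = ΔCt(sample) − ΔCt(calibrator), and relative expression = 2^(−D).
- Calibrator minus sample: D′ = −D, and relative expression = 2^(D′).

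The printed form is right under the second order and the reciprocal under the first. The documents state neither.

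**2. Size under the first order.**

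| ΔΔCt (sample − calibrator) | 2^(−ΔΔCt) | 2^(ΔΔCt), as printed |
|---|---|---|
| −2 | 4 | 0.25 |
| −1 | 2 | 0.5 |
| 0 | 1 | 1 |
| +1 | 0.5 | 2 |
| +2 | 0.25 | 4 |

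The two columns differ by a factor of 2^(2·|ΔΔCt|): 4 at one cycle, 16 at two.

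**3. Effect on the planned analyses.** log2 of 2^(−D) is −D, and log2 of 2^(D) is D. The analysed variable is multiplied by −1: coefficients and correlations change sign, while standard errors, two-sided p-values and the decision on the interaction stay the same. This takes the log transform to cover the correlations as well as the models, which is the natural reading.

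**4. Illustration.** One simulated data set used 22 per group, the plan's sample size. All other values are assumptions: ΔΔCt with SD 1.2 and a shift of −0.8 in the test group; attachment-level change equal to 0.4·ΔΔCt − 1 plus noise of SD 1.1; GCF equal to −0.5·ΔΔCt plus noise of SD 1.

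| Quantity | Minus sign | No minus sign |
|---|---|---|
| Group difference, natural log scale | +0.697 (p = 0.005) | −0.697 (p = 0.005) |
| r, log tissue with attachment change | −0.49 | +0.49 (same p) |
| r, log tissue with GCF | +0.61 | −0.61 (same p) |
| r, raw tissue with attachment change | −0.54 | +0.38 |
| Raw median | 1.27 | 0.79 |
| r, GCF with attachment change | −0.13 | −0.13 |

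Only rows that use tissue values move. On the log scale they move in sign alone; on the raw scale the size of the correlation changes too.

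**5. Calibrator.** With one common calibrator value c per gene, log2 fold change = −ΔCt + c. This differs from −ΔCt by a constant, so the tests of group, time and interaction, and the Pearson correlations, are the same whichever is modelled. With each patient's own baseline as calibrator, the baseline value is 0 and the 2-week value is −(ΔCt at 2 weeks − ΔCt at baseline). Under a common calibrator the within-patient change is (−ΔCt at 2 weeks + c) − (−ΔCt at baseline + c), which is the same quantity. With complete pairs the estimated group-by-time contrast therefore does not change. What would be lost is any tissue comparison or correlation at baseline, and the 2-week correlations would use change rather than level. The plan models each measure by group and time and correlates tissue with GCF by visit. That presupposes baseline values that vary, and so fits a common calibrator better.

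**The case for a change.** The strongest case for action is that the text, as read, has the wrong sign under the usual convention; that the missing definitions leave a reader unable to tell whether a value above 1 means up or down; and that a reversal would pass unnoticed because p-values do not change. Stating the sign and the calibrator would cost almost nothing.

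Part of this stands. The sign is absent from the text as read, the definitions are missing, and a literal computation with sample-minus-calibrator differences would give reciprocals and wrong raw medians.

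It does not go further, for three reasons. First, the sentence names a method and refers to a paper for the procedure, so the symbol works as a label. Secondly, the document describes finished work: it is dated March 2022, the trial ran from March 2019 to December 2020, and the laboratory section is in the past tense. No analyst is waiting to apply the printed exponent, and nothing shows that reciprocals were computed. Thirdly, the text comes from a PDF read by a program, and a small superscript minus is easily lost. The minus signs that survive in the storage temperatures are full-size characters and do not settle the matter.

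The prediction that tissue and GCF results would contradict each other has no support. It assumes that the two agree when correctly signed, but the documents give no results and do not list the genes on the array.

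**Conclusion.** No change to the plan follows. The missing minus is best read as a clerical slip in the name of a method, or as a loss in PDF reading. The undefined reference gene and calibrator are laboratory detail of the kind that analysts fill sensibly from the cited procedure.

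At worst, if the original page also lacks the sign, if ΔΔCt is sample minus calibrator, and if the symbol was followed to the letter, RT-PCR fold changes would be inverted and RT-PCR effects and correlations would change sign. The reach stops there. GCF models, GCF correlations with attachment change, the bleeding analysis, the primary outcome and all two-sided log-scale p-values would be unaffected. Modelling −ΔCt instead would give the same tests as the planned log transform under a common calibrator, so it brings no gain.

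This rests on two assumptions that the documents cannot confirm: that the cited procedure, which I have not seen, defines its exponent consistently with its own order of subtraction, and that the laboratory followed it.
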